8.1. Primary Immunogenicity Analysis

The primary immunogenicity endpoints HAI, Neut and NAI seroconversion, percentage of subjects with titer $\geq 1:40$ for HAI and Neut only, GMTs, ratios of GMTs between adjuvanted and unadjuvanted groups, and GMFRs against the 2018/2019 QIV strains 28 days after study vaccination (Day 29) will be summarized as described above. The primary analysis population will be mITT, with results from the PP population providing a comparison of the sensitivity of immunogenicity results to subject adherence to protocol-defined conditions.

Summaries of primary immunogenicity endpoints are presented for the 2018/2019 QIV strains in [Table 21](#), [Table 22](#), [Table 23](#), [Table 24](#), [Table 25](#), [Table 26](#), [Table 27](#), and [Table 28](#) for HAI, [Table 29](#), [Table 30](#), [Table 31](#), [Table 32](#), [Table 33](#), [Table 34](#), [Table 35](#), and [Table 36](#) for Neut, and [Table 53](#), [Table 54](#), [Table 55](#), [Table 56](#), [Table 57](#), [Table 58](#), [Table 59](#), and [Table 60](#) for NAI.

8.2. Secondary Immunogenicity Analyses

The secondary immunogenicity endpoints HAI, Neut and NAI seroconversion, percentage of subjects with titer $\geq 1:40$ for HAI, GMFRs, GMTs, and ratios of GMTs (between adjuvanted group and unadjuvanted) against the 2019/2020 QIV strains 28 days after vaccination with the 2019/2020 QIV (Day 118) will be summarized as described above. HAI and Neut seroconversion, percentage of subjects with HAI titers $\geq 1:40$, GMFRs, GMTs, and ratios of GMTs for HAI and Neut against heterologous influenza A/H3 strains on approximately Days 8, 29, 57, 90, and 118 after study vaccination with the 2018/2019 QIV will be also presented. HAI, Neut and NAI seroconversion, percentage of subjects with HAI and Neut titers $\geq 1:40$, and GMTs against the 2018/2019 QIV strains on approximately Days 8, 29, 57, 90, and 118 after study vaccination will be presented. HAI, Neut, and NAI GMFRs against the 2018/2019 QIV strains on approximately Day 57 and Day 90 will also be presented. NAI seroconversion, NAI GMTs and ratios of NAI GMTs against heterologous N1 and N2 NA antigens will also be assessed on approximately Days 8, 29, 57, 90, and 118 for study groups 1, 2 and 3. No formal hypothesis testing is planned.

Secondary summaries for the 2019/2020 QIV strains are provided in [Table 69](#), [Table 70](#), [Table 71](#), [Table 72](#), [Table 73](#), [Table 74](#), [Table 75](#), [Table 76](#), [Table 77](#), [Table 78](#), [Table 79](#), and [Table 80](#). Summaries of HAI, and Neut against heterologous H3 Influenza strains for both mITT and PP populations will also be provided in [Table 81](#), [Table 82](#), [Table 83](#), [Table 84](#), [Table 85](#), [Table 86](#), [Table 87](#), [Table 88](#), [Table 89](#), and [Table 90](#) for HAI, and [Table 91](#), [Table 92](#), [Table 93](#), [Table 94](#), [Table 95](#), [Table 96](#), [Table 97](#), and [Table 98](#) for Neut. Summaries of NAI against heterologous N1 and N2 antigens will be presented in [Table 99](#), [Table 100](#), [Table 101](#), [Table 102](#), [Table 103](#), [Table 104](#), [Table 105](#), [Table 106](#), [Table 107](#), [Table 108](#), [Table 109](#), and [Table 110](#).

Reverse cumulative distribution (RCD) curves will be presented for baseline and post-vaccination HAI, Neut and NAI antibody titers against 2018/2019 and 2019/2020 QIV strains, HAI and Neut antibody titers against heterologous influenza A/H3 strains, and NAI antibody titers against heterologous N1 and N2 NA antigens. Plots for titers HAI, Neut, and NAI titers against the 2018/2019 QIV strains will be generated with eight panels (Day 1 (Baseline), Day 8, Day 29, Day 57, Day 90, and Day 118), and separate curves within each panel for each study arm, as shown beginning with [Figure 2](#), and ending with [Figure 25](#). RCD curves for HAI, Neut, and NAI against the 2019/2020 QIV strains will be generated with four panels (Day 90 (Baseline) and Day 118) and be presented starting with [Figure 26](#), and ending with [Figure 49](#). In a similar manner, RCD curves of HAI titers against heterologous influenza A/H3 strains will be presented in [Figure 50](#), [Figure 51](#), [Figure 52](#), [Figure 53](#), [Figure 54](#), [Figure 55](#), [Figure 56](#), [Figure 57](#), [Figure 58](#), and [Figure 59](#), and those for Neut titers against heterologous influenza A/H3 strains in [Figure 60](#), [Figure 61](#), [Figure 62](#), [Figure 63](#), [Figure 64](#), [Figure 65](#), [Figure 66](#), [Figure 67](#), [Figure 68](#), and [Figure 69](#) for Neut. RCD curves of NAI titers against heterologous N1 and N2 NA antigens will be presented in [Figure 70](#), [Figure 71](#), [Figure 72](#), [Figure 73](#), [Figure 74](#), [Figure 75](#), [Figure 76](#), [Figure 77](#), [Figure 78](#), [Figure 79](#), [Figure 80](#), and [Figure 81](#).

Geometric Mean Titers of HAI, Neut, and HAI against 2018/2019 QIV strains by study day and study arm will be plotted in [Figure 82](#), [Figure 83](#), [Figure 84](#), [Figure 85](#), [Figure 86](#), and [Figure 87](#).

8.3. Exploratory Immunogenicity Analyses

The exploratory immunogenicity endpoints HAI, Neut and NAI seroconversion, percentage of subjects with titer $\geq 1:40$ for HAI, GMFRs, GMTs, and ratios of GMTs (between adjuvanted group and unadjuvanted) against the 2019/2020 QIV strains 28 days after vaccination with the 2019/2020 QIV (Day 118) will be summarized as described above. HAI and Neut seroconversion, percentage of subjects with HAI titers $\geq 1:40$, GMFRs, GMTs, and ratios of GMTs for HAI and Neut against heterologous influenza A/H3 strains on approximately Days 180 and 365 after study vaccination with the 2018/2019 QIV will be also presented. HAI, Neut and NAI seroconversion, percentage of subjects with HAI and Neut titers $\geq 1:40$, and GMTs against the 2018/2019 QIV strains on approximately Days 180 and 365 after study vaccination will be presented. NAI seroconversion, NAI GMTs and ratios of NAI GMTs against heterologous N1 and N2 NA antigens will also be assessed on approximately Days 180 and 365 for study groups 1, 2 and 3. No formal hypothesis testing is planned.

Summaries of HAI, and Neut against heterologous H3 Influenza strains for both mITT and PP populations for Days 180 and 365 will also be provided in [Table 81](#), [Table 82](#), [Table 83](#), [Table 84](#), [Table 85](#), [Table 86](#), [Table 87](#), [Table 88](#), [Table 89](#), and [Table 90](#) for HAI, and [Table 91](#), [Table 92](#), [Table 93](#), [Table 94](#), [Table 95](#), [Table 96](#), [Table 97](#), and [Table 98](#) for Neut. Summaries of NAI against heterologous N1 and N2 antigens for Days 180 and 365 will be presented in [Table 99](#), [Table 100](#), [Table 101](#), [Table 102](#), [Table 103](#), [Table 104](#), [Table 105](#), [Table 106](#), [Table 107](#), [Table 108](#), [Table 109](#), and [Table 110](#).

Reverse cumulative distribution (RCD) curves will be presented for baseline, Day 180, and Day 365 HAI, Neut and NAI antibody titers against 2018/2019 and 2019/2020 QIV strains, HAI and Neut antibody titers against heterologous influenza A/H3 strains, and NAI antibody titers against heterologous N1 and N2 NA antigens. Two panels will be added to figures described in Section 8.2 to add Day 180 and Day 365 timepoints.

Immunogenicity data summaries and analysis for the following exploratory endpoints will be presented for the PP populations. Immunogenicity results from the subgroup analysis by baseline serostatus for 2018/2019 QIV strains will be presented in [Table 37](#), [Table 38](#), [Table 39](#), and [Table 40](#) for HAI, [Table 41](#), [Table 42](#), [Table 43](#), and [Table 44](#) for Neut, and [Table 61](#), [Table 62](#), [Table 63](#), and [Table 64](#) for NAI. Similarly, subgroup results by previous vaccination will be presented in [Table 45](#), [Table 46](#), [Table 47](#), and [Table 48](#) for HAI, [Table 49](#), [Table 50](#), [Table 51](#), and [Table 52](#) for Neut, and [Table 65](#), [Table 66](#), [Table 67](#) and [Table 68](#) for NAI. Subgroup analysis results for HAI, Neut, and NAI against 2019/2020 QIV strains are presented in [Table 71](#), [Table 72](#), [Table 75](#), [Table 76](#), [Table 79](#), and [Table 80](#). Summary statistics for influenza specific IgG, IgM, and IgA B memory cells will be presented in [Table 111](#), [Table 112](#), and [Table 113](#). Summary statistics including the mean, GM, and mean absolute difference for influenza specific plasmablasts and Tfh cells will be presented in [Table 114](#), and [Table 115](#), respectively. GMT and GMFRs of functioning non-neutralizing Fc-effector antibodies Against 2018/2019 QIV Strains will be provided in [Table 116](#).

Plots for HA and NA binding antibodies against different H3 strains will be presented in [Figure 88](#) and [Figure 89](#).

Association of non-neutralizing Fc-effector antibody titers and HAI antibody titers, HAI seroconversion, and HAI seroprotection against 2018/2019 QIV strains are presented in [Figure 90](#), [Figure 92](#), and [Figure 94](#). Similar plots are generated for the association of non-neutralizing Fc-effector antibody titers and Neut antibody titers, Neut seroconversion, and Neut seroprotection against 2018/2019 QIV strains and presented in [Figure 91](#), [Figure 93](#), and [Figure 95](#).

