### **11.6.3 Humoral Immunogenicity Data**

Summaries and analysis of immunogenicity data will be presented for the mITT and PP populations.

Immune responses in terms of strain-specific HAI, NAI, and Neut antibody titers will be summarized by treatment arm at each time point. Analyses will include GMTs, ratio of GMTs between adjuvanted and unadjuvanted study arms, percentage of subjects achieving seroconversion (as defined in Table 1) and percentage of subjects with a titer  $\geq 1:40$  (HAI and Neut only) along with corresponding 95% confidence intervals. Descriptive summary statistics will be provided for all assays and time points. These immune responses against vaccine strains will also be presented by serostatus and previous influenza vaccination. The correlation between

HAI, NAI and Neut antibody titers will be evaluated. Plots such as reverse cumulative distributions or longitudinal presentations of GMTs will be presented.

Further immunogenicity testing and/or analyses may be carried out in the future based upon subjects' prior receipt of non-seasonal influenza vaccines, including type (inactivated or live attenuated), what subtype (e.g. A/H3, A/H5, A/H9) and approximate date of vaccination.

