#### **11.6.4 Exploratory Cellular Immunogenicity Data**

Summaries of exploratory cellular immunology assays will be presented for the Per Protocol Population and will be presented overall as well as by treatment arm.

Analysis of the exploratory cellular immunogenicity data will be primarily descriptive. Association of exploratory endpoints with HAI, NAI, and Neut antibody titers will be assessed.

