8. IMMUNOGENICITY EVALUATION

Immunogenicity data summaries and analysis for primary and secondary endpoints will be presented for the mITT and PP populations. Immune responses in terms of strain-specific 2018/2019, 2019/2020 QIV HAI, NAI, and Neut antibody titers will be summarized by study arm at each time point. Descriptive summary statistics will be provided for all assays and time points including number of subjects with non-missing results, percentage of subjects with titers $\geq 1:40$ for HAI and Neut only, percentage of subjects achieving seroconversion, GMTs along with corresponding 95% CI, and GMFRs along with corresponding 95% CI. Exact confidence intervals using the Clopper Pearson method will be presented for proportional endpoints. Ratios of GMTs along with their 95% CIs between adjuvanted and unadjuvanted groups will be presented at each timepoint. Confidence intervals using the Delta Method will be provided for the ratio of GMTs.

Individual HAI, NAI, and Neut assay results will be provided in [Listing 9](#), [Listing 10](#), and [Listing 11](#). Individual exploratory assay results will be provided in [Listing 12](#), [Listing 13](#), and [Listing 14](#) for memory B cells, [Listing 15](#) for Tfh cells, [Listing 16](#) for plasmablasts, [Listing 17](#) for neutralizing fc-effector, [Listing 18](#) for antibody forensics, and [Listing 19](#) for NA ELISA.

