12. SUMMARY OF CHANGES IN THE CONDUCT OF THE STUDY OR PLANNED ANALYSES

This SAP includes one change from the analyses described in the protocol. Logistic regression will be used instead of the Chi-Square or Fisher's exact test to model the relationship of treatment with reporting any local or systemic events post vaccination. Besides providing the strength of the association between the treatment and probability of reporting any local or systemic event in terms of odds ratio, logistic regression also provides a prediction model for the probability of a local or solicited event occurring given the subject's study arm. Version 3.0 of the SAP includes moving Day 180 and Day 365 immunogenicity endpoints from secondary to exploratory endpoints and the addition of a topline report.

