Seroconversion - % (95% CI)	xx (xx, xx)	xx (xx, xx)	xx (xx, xx)	xx (xx, xx)	xx (xx, xx)	xx (xx, xx)	xx (xx, xx)	xx (xx, xx)	xx (xx, xx)	xx (xx, xx)	xx (xx, xx)	xx (xx, xx)
Titer ≥ 1:40 - % (95% CI)	xx (xx, xx)	xx (xx, xx)	xx (xx, xx)	xx (xx, xx)	xx (xx, xx)	xx (xx, xx)	xx (xx, xx)	xx (xx, xx)	xx (xx, xx)	xx (xx, xx)	xx (xx, xx)	xx (xx, xx)
GMFR (95% CI)	xx.x (xx.x,xx.x)	xx.x (xx.x,xx.x)	xx.x (xx.x,xx.x)	xx.x (xx.x,xx.x)	xx.x (xx.x,xx.x)	xx.x (xx.x,xx.x)	xx.x (xx.x,xx.x)	xx.x (xx.x,xx.x)	xx.x (xx.x,xx.x)	xx.x (xx.x,xx.x)	xx.x (xx.x,xx.x)	xx.x (xx.x,xx.x)
Day 365 Post Vaccination 1												
n	x	x	x	x	x	x	x	x	x	x	x	x
GMT (95% CI)	xxx.x (xxx.x,xxx.x)	xxx.x (xxx.x,xxx.x)	xxx.x (xxx.x,xxx.x)	xxx.x (xxx.x,xxx.x)	xxx.x (xxx.x,xxx.x)	xxx.x (xxx.x,xxx.x)	xxx.x (xxx.x,xxx.x)	xxx.x (xxx.x,xxx.x)	xxx.x (xxx.x,xxx.x)	xxx.x (xxx.x,xxx.x)	xxx.x (xxx.x,xxx.x)	xxx.x (xxx.x,xxx.x)
Ratio of GMTs (95% CI) ^a	-	-	xx.x (xx.x,xx.x)	xx.x (xx.x,xx.x)	xx.x (xx.x,xx.x)	xx.x (xx.x,xx.x)	-	-	xx.x (xx.x,xx.x)	xx.x (xx.x,xx.x)	xx.x (xx.x,xx.x)	xx.x (xx.x,xx.x)
Seroconversion - % (95% CI)	xx (xx, xx)	xx (xx, xx)	xx (xx, xx)	xx (xx, xx)	xx (xx, xx)	xx (xx, xx)	xx (xx, xx)	xx (xx, xx)	xx (xx, xx)	xx (xx, xx)	xx (xx, xx)	xx (xx, xx)
Titer ≥ 1:40 - % (95% CI)	xx (xx, xx)	xx (xx, xx)	xx (xx, xx)	xx (xx, xx)	xx (xx, xx)	xx (xx, xx)	xx (xx, xx)	xx (xx, xx)	xx (xx, xx)	xx (xx, xx)	xx (xx, xx)	xx (xx, xx)
GMFR (95% CI)	xx.x (xx.x,xx.x)	xx.x (xx.x,xx.x)	xx.x (xx.x,xx.x)	xx.x (xx.x,xx.x)	xx.x (xx.x,xx.x)	xx.x (xx.x,xx.x)	xx.x (xx.x,xx.x)	xx.x (xx.x,xx.x)	xx.x (xx.x,xx.x)	xx.x (xx.x,xx.x)	xx.x (xx.x,xx.x)	xx.x (xx.x,xx.x)

N = Number of subjects in the Modified Intent-to-Treat Population; n = Number of subjects with available results; GMT = Geometric Mean Titer; GMFR = Geometric Mean Fold Rise.

^aRatio of GMTs is defined as the ratio of the GMT from the adjuvanted group divided by the GMT from the corresponding unadjuvanted group. Confidence intervals for the ratio of GMTs will use the Delta Method.

Tables with similar format

- Table 38:** Summaries of Hemagglutination Inhibition Antibody Against 2018/2019 QIV Strain A/Singapore/INFIMH-16-0019/2016 IVR-186 (H3N2) by Study Day, Study Arm, and Baseline Serostatus, Per Protocol Population
- Table 39:** Summaries of Hemagglutination Inhibition Antibody Against 2018/2019 QIV Strain B/Phuket/3073/2013 (B Yamagata lineage) by Study Day, Study Arm, and Baseline Serostatus, Per Protocol Population

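### The SAP limits the humoral subgroup tables to the per-protocol population, without declaring it, where the protocol presents them for both mITT and PP

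*SAP*

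**What the plan says.** Protocol 11.6.3 sets one rule for humoral data: "Summaries and analysis of immunogenicity data will be presented for the mITT and PP populations". The same section adds: "These immune responses against vaccine strains will also be presented by serostatus and previous influenza vaccination". It states no exception for the subgroups. The protocol uses PP alone in the next section, for a different class of assay: "Summaries of exploratory cellular immunology assays will be presented for the Per Protocol Population".

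The SAP splits this differently. Section 8 says: "Immunogenicity data summaries and analysis for primary and secondary endpoints will be presented for the mITT and PP populations". Section 8.1 ranks the two populations: "The primary analysis population will be mITT", with PP as the sensitivity check. Section 8.3 then places the HAI, Neut and NAI subgroup tables together with the cellular and Fc-effector assays under: "Immunogenicity data summaries and analysis for the following exploratory endpoints will be presented for the PP populations". Section 12 opens with: "This SAP includes one change from the analyses described in the protocol". That change is logistic regression for solicited events. Section 12 also records two Version 3.0 items: the move of the Day 180 and Day 365 endpoints, and the topline report.

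SAP 6.4 describes the subgroup analyses as exploratory and not adequately powered, and names no population for them.

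**The concern.** SAP 6.3 defines the two populations differently. mITT groups subjects by randomised arm. PP groups them by vaccine received and removes visit data for reasons that arise after randomisation, such as intercurrent vaccines, immunosuppressive therapy and out-of-window visits. Randomisation is stratified by previous seasonal influenza vaccination (protocol 5.2.1, SAP 4.4.3), so comparing arms within a prior-vaccination stratum in mITT keeps subjects in the arms to which they were randomised in that stratum. The PP comparison does not guarantee this. In the subgroups the plan keeps only the population that it elsewhere treats as the sensitivity check, and a reader of SAP 12 would not know that the protocol had asked for more.

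The table shells add a smaller problem. Subgroup tables titled for the PP population carry a footnote that defines the column N as mITT, so title and footnote give a programmer two different instructions.

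**Working it through.** The documents state no figure to reproduce. The check is a comparison of text, with some arithmetic for scale.

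**1. Which tables are affected.** Every subgroup table is titled for PP, and no mITT counterpart is listed.
- Prior vaccination: Tables 45-52 (8), 65-68 (4), and 72, 76, 80 (3). Total 8 + 4 + 3 = 15.
- Day 1 serostatus, 2018/2019 strains: Tables 37-44 (8) and 61-64 (4). Total 12.
- Serostatus, 2019/2020 strains: Tables 71, 75, 79 (3). SAP 3.2 takes the pre-vaccination titer for these strains from Day 90, which is after randomisation and after the adjuvanted dose.

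**2. Whether exploratory status explains it.** It does not. SAP 8.3 presents other exploratory humoral results, the Day 180 and Day 365 titers against heterologous H3 strains, for both populations.

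**3. Scale at Day 29.** Protocol 11.4.2 expects about 3% loss or exclusion: 40 × 0.97 = 38.8, planned as 38. PP could then be smaller than mITT by up to 40 − 38 = 2 per arm, or 2 × 6 = 12 overall. This is an upper planning figure, because the 3% includes subjects lost to follow-up, who have no Day 29 result under mITT either. The documents give no split by serostatus or prior vaccination, so subgroup sizes are unknown.

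**4. What one excluded subject can do (illustration only).** Removing one of n subjects who lies d SD from the cell mean moves the log mean by d/(n − 1) SD. In standard errors of the full cell (SD/√n) the shift is d√n/(n − 1). Assume n from 10 to 30 and d from 0.8 to 2:
- n = 10: 0.28 (d = 0.8) to 0.70 (d = 2) standard errors
- n = 20: 0.19 to 0.47
- n = 30: 0.15 to 0.38

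**5. Later visits.** The gap between populations may be larger at Day 118. The Day 90 window is 90 ± 14, so Day 76 to Day 104. SAP 6.3.3 drops Visit 7 data before Day 114 or after Day 122. If sites bleed 28 days after the second vaccination, a subject vaccinated on Day 76 is sampled on Day 76 + 28 = 104 and leaves PP; one vaccinated on Day 104 is sampled on Day 132 and also leaves. Only second vaccinations on Days 86 to 94 (114 − 28 and 122 − 28) stay in. If sites instead follow the nominal Day 118 ± 3 from the first vaccination, this loss does not arise. The documents do not say how many subjects would be affected.

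**6. Footnotes.** All ten fully drawn subgroup shells (Tables 37, 45, 61, 65, 71, 72, 75, 76, 79, 80) and Table 116 are titled for PP but carry: "N = Number of subjects in the Modified Intent-to-Treat Population; n = Number of subjects with available results". Tables 111 and 114 define N as PP, which matches their titles. SAP 6.1 asks for the population size relevant to each table.

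**The case against.** The case for leaving this alone is reasonable in several respects.

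- *A reader might infer that the randomised comparison is lost.* The documents do not support that. Overall mITT results stay primary for every assay and 2018/2019 strain. mITT is also not all randomised subjects: it requires the first vaccination and at least one valid post-vaccination result. Only the mITT version of exploratory, unpowered subgroup tables is missing.
- *A reader might infer that the subgroup counts cannot be reconciled.* They can be, to the planned PP tables by arm (25-28, 33-36, 57-60, 70, 74, 78), though not to the mITT tables.
- *A reader might infer that the footnote makes estimates wrong or hides exclusions.* It does not. Each block of rows reports n with available results, Table 12 gives PP exclusions by visit and reason, and Listing 5 shows whether results were available for excluded subjects.
- *A reader might infer a sizeable bias.* The illustration above stays below one standard error even with an extreme subject in a small cell, and it rests on assumed cell sizes and distances.
- *The randomisation-stratum argument does not reach every table.* It covers the 15 prior-vaccination tables. For the 12 Day 1 serostatus tables the argument is consistency with the protocol. For Tables 71, 75 and 79 the subgroup itself is defined after randomisation, so mITT does not restore a randomised comparison.

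It can also be said that protocol 11.6.3 names the populations once, generally, and not in the subgroup sentence. But that sentence sits under the general rule, and the protocol says so where it means PP alone. The undeclared difference stands.

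**Conclusion.** The SAP departs from protocol 11.6.3 by restricting the serostatus and prior-vaccination breakdowns to PP, and SAP 12 does not declare it. The consequence is limited: the as-randomised version of exploratory subgroup results is absent, in a plan that makes mITT primary and stratifies randomisation on one of the two subgroup factors. No primary or overall result changes. Neither the direction nor the size of any difference between the mITT and PP subgroup results can be derived from the documents. The gap of 2 per arm at Day 29 is an upper planning figure, and the Day 118 loss depends on how sites time that visit. The footnote error is separate and purely one of labelling. The point is worth correcting because the protocol already specifies the missing analysis and the programs exist.

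**What to change.** 1. In SAP 8.3, present the prior-vaccination tables (45-52, 65-68, 72, 76, 80) for mITT as randomised, with PP as the sensitivity version.
2. Do the same for the Day 1 serostatus tables (37-44, 61-64), among mITT subjects with a baseline titer. State that restriction: SAP 6.3.2 does not require a baseline for mITT, although the Table 12 shell lists a missing baseline as an mITT exclusion.
3. For Tables 71, 75 and 79, either add mITT or declare and justify PP-only in SAP 12.
4. In every PP-titled shell, including Table 116 and those described as copies of an mITT shell, make the footnote's N the population named in the title.

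Cost: steps 1 and 2 add 15 + 12 = 27 tables from existing programs, or none if mITT replaces PP. Adding mITT under step 3 brings the total to 27 + 3 = 30. Step 4 is a text edit. Nothing changes in trial conduct or data collection.
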